2.0 LIST OF ABBREVIATIONS

AE	Adverse Event			
CMS Centralized Monitoring Service				
CRF	Case Report Form			
CTCAE	Common Terminology Criteria for Adverse Events			
DSMP	Data & Safety Monitoring Plan			
eCRF	Electronic Case Report Forms			
EHR	Electronic Health Record			
FDA	Food and Drug Administration			
GCP	Good Clinical Practice			
HIPAA	Health Insurance Portability and Accountability Act			
IND	Investigational New Drug Application			
IRB	Institutional Review Board			
OnCore	Online Collaborative Research Environment			
PHI	Protected Health Information			
PI	Principal Investigator			
pIMDs	Potential Immune-Mediated Diseases			
PRC	Pharmaceutical Research Center			
REDCap	Research Electronic Data Capture			
SAE	Serious Adverse Event			
SAP	Statistical Analysis Plan			
SMP	Study Monitoring Plan			
UP	Unanticipated Problem			

3.0 SYNOPSIS

Full Title	Additional Recombinant COVID-19 Humoral and Cell-Mediated Immunogenicity in Immunosuppressed Populations				
Short Title	ARMOR-COVID				
Protocol Number	Oncore Protocol number: 235058 IRB Protocol number: 2023-1208				
ClinicalTrials.gov Identifier & Summary	NCT06027229 To determine whether providing a 2023/2024 (monovalent, XBB containing) Novavax COVID-19 vaccine, the Omicron XBB.1.5 vaccine is named BV2601, with the drug product as NVX-CoV2601, improves sustained humoral and cell-mediated immunogenicity against SARS-CoV-2 in immunosuppressed patients with IBD and/or solid organ transplant recipients. The study will be extended to 2024/2025 season which will determine whether providing a 2024/2025 (monovalent, XBB containing) Novavax COVID-19 vaccine, the Omicron XBB.1.5 vaccine is named BV2601, with the drug product as NVX-CoV2024-2025, improves sustained humoral and cell-mediated immunogenicity against SARS-CoV-2 in immunosuppressed patients with IBD and/or solid organ transplant recipients.				
Number of Site(s)	One clinical site in the United States.				
Phase	Phase II				
Main Inclusion Criteria	 Patient is between the ages of 18-85 years. Patients has a history of ulcerative colitis (UC), Crohn's disease, or pouchitis diagnosed by standard clinical, radiographic, endoscopic, and histopathologic criteria or solid organ transplant recipient. Have received at least three doses of a COVID-19 vaccine. On systemic immunosuppressive therapy for inflammatory bowel disease or for solid organ transplant 				
Main Exclusion Criteria	 Allergy to recombinant COVID-19 vaccine or any component of it Patient cannot or will not provide written informed consent. Unable to provide appropriate informed consent because of illiteracy or impairment in decision-making capacity. Active antibody-mediated or cellular rejection. Recent IBD flare requiring initiation of systemic corticosteroids within the past month. 				
Objective(s)	Primary Objective Humoral Immunogenicity of a NVX-CoV2601 Secondary Objectives Sustained antibody concentrations of the NVX-CoV2601 booster dose. Seroconversion. Cell-mediated immunity to NVX-CoV2601 booster vaccine Sustained cell-mediated immunity to the NVX-CoV2601booster vaccine. Describe the safety of the NVX-CoV2601.				

- Evaluate the disease activity following administration of the booster dose up to 30 days post-last vaccination and during the whole post-vaccination follow-up period.
- Evaluate for solid organ transplant rejection following administration of booster dose, up to 30 days post-vaccination and during the whole post-vaccination follow-up period

2024-2025 season

(The 2024-2025 season activities will not proceed as originally planned due to the withdrawal of financial support from our sponsor).

Primary Objective

• Humoral Immunogenicity of a *NVX-CoV2024-2025 booster*

Secondary Objectives

- Sustained antibody concentrations of the NVX-CoV2024-2025 booster.
- Seroconversion.
- Cell-mediated immunity to NVX-CoV2024-2025 booster
- Sustained cell-mediated immunity to the NVX-CoV2024-2025 booster
- Describe the safety of the NVX-CoV2024-2025 booster
- Evaluate the disease activity following administration of the booster dose up to 30 days post-last vaccination and during the whole post-vaccination follow-up period.
- Evaluate for solid organ transplant rejection following administration of booster dose, up to 30 days post-vaccination and during the whole post-vaccination follow-up period

2023-2024 Season

Primary Endpoint

Antibody concentrations at V2 are statistically significantly higher than at V1.

Secondary Endpoints

- Seropositivity rate at V2 and V3 in all participants.
- Individuals who achieve seroconversion at V2
- Interferon gamma responses at V2 compared to V1.
- Interferon gamma responses at V3 compared to V1.
- The number and percentage of subjects reporting solicited and unsolicited AEs, pIMDs, and SAEs.
- Number and percentage of participants reporting disease flares of IBD.
- Number and percentage of participants reporting acute rejection of their transplant.

2024-2025 Season

Primary Endpoint

Antibody concentrations at V2 are statistically significantly higher than at V1.

Secondary Endpoints

Endpoints

	 Seropositivity rate at V2 and V3 in all participants. Individuals who achieve seroconversion at V2 Interferon gamma responses at V2 compared to V1. Interferon gamma responses at V3 compared to V1. The number and percentage of subjects reporting solicited and unsolicited AEs, pIMDs, and SAEs. Number and percentage of participants reporting disease flares of IBD. Number and percentage of participants reporting acute rejection of their transplant.
Study Design	2023-2024 season This will be a single-center, prospective, unblinded, non-randomized study of 120 immunosuppressed patients who are planning to receive a NVX-CoV2601 COVID-19 vaccine booster dose. 2024-2025 season
	This will be a single-center, prospective, unblinded, non-randomized study of 120 immunosuppressed patients who are planning to receive a NVX-CoV2024-2025 COVID-19 booster
FDA Regulatory Overview	The protocol uses an investigational product, NVX-CoV2601, and is being conducted under IND NUMBER 29913 that is held by [name].
Study Intervention	NVX-CoV26012023/2024 (monovalent, XBB containing) Novavax COVID-19 vaccine, the Omicron XBB.1.5 vaccine is named BV2601 NVX-CoV2024-2025 booster Novavax COVID-19 vaccine, the Omicron XBB.1.5 vaccine is named BV2601
Total Number of Subjects	2023-2024 season 21 patients were enrolled in this season 2024-2025 season (none will be recruited anymore) (The 2024-2025 season activities will not proceed as originally planned due to the withdrawal of financial support from our sponsor). A total 120 subjects will be enrolled.
Ota-la B	A total of 141 subjects will be enrolled for this study for both seasons.
Study Population	Male and females aged 18 to 85 with IBD and/or who are solid organ transplant recipients.
Statistical Methodology	In analyzing the primary endpoint, a paired t-test will be utilized to test whether, on average, there is a change of at least 15% antibody blood concentration between the first and second

	blood draws. A test statistics and degrees of freedom, including the 95% confidence intervals will be reported. In addition, we will model the post measurement blood draw concentrations (i.e., V2 and V3) as the response variable using an ANOVA (i.e., ANOVA-POST), while adjusting for the initial responses (V1) and other baseline covariates.
Estimated Subject Duration	The duration of the study for each subject is approximately 6 months.
Estimated Enrollment Period & Study Duration	Study enrollment and follow-up will occur over 6 months with the total expected duration of the trial to be 24 months.

5.0 INTRODUCTION

5.1 Background and Scientific Rationale

Immunosuppressed populations, which include patients with inflammatory bowel disease (IBD) and those with solid organ transplant (such as liver transplant recipients), account for approximately 3% of the population in the United States (US).1 They are commonly treated with immunosuppressive medications that can increase their risk of respiratory infections such as influenza, invasive pneumococcal disease and SARS-CoV-2 all which are potentially vaccine preventable diseases.² Coronavirus disease 2019 (COVID-19) has resulted in a global pandemic million infections and more than 6 million deaths worldwide. with greater than 500 Immunosuppressed populations are at an increased risk for severe COVID-19 outcomes. Three safe and highly efficacious SARS-CoV-2 vaccines are authorized by the Food and Drug Administration (FDA) in response to the COVID-19 pandemic. Immunosuppressed patients were excluded from the original Phase III clinical trials; therefore, the efficacy in this population is unknown. These vaccines have been found to be safe in patients with IBD, with similar rates of localized and systemic adverse events as found in the general population, with low rates of IBD flares following vaccination (2%). 3,4 Additionally these vaccines are associated with similar rates of reactogenicity in solid organ transplant recipients and low rates of acute rejection following immunization. 5, 6

Patients with solid organ transplant are less likely to seroconvert after the two-dose series. The humoral response to COVID-19 vaccines in patients with solid organ transplant has been reported to be approximately 50-70%. In contrast, it appears that most patients with IBD are able to mount an antibody response post immunization. In our study HERCULES we found that patients with IBD had lower antibody concentrations than healthy controls. These studies have raised concerns that immunosuppressed patients may be susceptible to breakthrough COVID-19 infections and potential complications from COVID-19 disease despite being immunized. Our study HERCULES showed robust antibody responses after three doses of COVID-19 vaccines in patients with IBD, with antibody concentrations being higher after the third dose than after the two doses primary series. In contrast, among immunosuppressed solid organ transplant recipients, a third dose improves humoral immune response but they are still suboptimal when compared to the general population.

There is evidence of waning humoral immunity in the general population following vaccination, especially in those who are immunosuppressed or greater than 65 years. A high incidence of breakthrough infection among vaccinated healthcare workers has also been described. As such, the Advisory Committee on Immunization Practice (ACIP) recommended a booster mRNA vaccine dose five months after completion of the original two-dose vaccine series for all adults. Booster doses have reduced the incidence of infection and severity of illness. For those who completed a three-dose mRNA vaccine primary series, as recommended by the ACIP for those who are moderately to severely immunosuppressed, are now eligible for up to two additional booster doses.

Homologous booster strategies have improved vaccine response in the general population and immunosuppressed populations. Heterologous prime boost strategies may offer immunological advantages to optimize the breadth and longevity of protection achieved with the currently available vaccines. A recent study showed that both homologous and heterologous boosting strategies resulted in improved humoral immunogenicity in adults. Furthermore a large population based study showed that heterologous boosting achieved higher vaccines effectiveness for many clinical outcomes compared to homologous boosting. If the general population and immunosuppressed populations achieved with the currently available vaccines and the general population and immunosuppressed populations. Heterologous prime boost strategies may offer immunological advantages to optimize the breadth and longevity of protection achieved with the currently available vaccines. A recent study showed that both homologous and heterologous boosting achieved higher vaccines effectiveness for many clinical outcomes compared to homologous boosting.

A new COVID-19 vaccine, NVX-CoV2372 (Novavax), made up of a full-length stabilized recombinant spike protein, has been found to be safe and effective in preventing COVID-19.18 It recently received approval from the FDA for emergency use authorization (EUA). The ACIP also recommended the use of this vaccine as a primary series. This recombinant COVID-19 vaccine may be an ideal agent to boost, given that it has a different mechanism and has the full length of the spike protein compared to mRNA vaccines. Thus, there is a critical need to evaluate whether a recombinant COVID-19 vaccine can improve the immune response to COVID-19 vaccines in immunosuppressed populations. The goal of this study to evaluate the immunogenicity of a 2023/2024 and 2024/2025 (monovalent, XBB containing) Novavax COVID-19 vaccine, the Omicron XBB.1.5 vaccine is named BV2601 with the drug product as NVX-CoV2601 and not to evaluate the impact of a heterologous boosting strategy. This critical need will be addressed via a collaborative study with investigators in expertise in inflammatory bowel disease and vaccinology ([name], DO, MS), vaccinology ([name], MPH), and immunology ([name]). Whether antibody concentrations will continue to wane after booster doses of mRNA vaccines and increase the risk of breakthrough infections in immunosuppressed patients remains unknown. Thus, there is a critical need to continue investigating ways to improve sustained protection in these populations. We will help answer this critical question with the following aims.

5.2 Study Aim and Hypotheses.

Aim 1: To determine whether providing a NVX-CoV2601 booster COVID-19 vaccine improves sustained humoral and cell-mediated immunogenicity against SARS-CoV-2 in immunosuppressed patients with IBD and/or solid organ transplant recipients.

We hypothesize that solid organ transplant recipients receiving a combination of immunosuppressive regimens will have lower antibody concentrations than patients with IBD because our previous work has shown that patients with IBD have higher rates of seroconversion than solid organ transplant recipients.

6.0 STUDY OBJECTIVES & ENDPOINTS

The vaccine will be evaluated for two seasons separately: 2023/2024 and 2024/2025. Thus, we will have two co primary objectives.

• 2023-2024 season

The primary objective of this study is to evaluate the immunogenicity of a 2023/2024 (monovalent, XBB containing) Novavax COVID-19 vaccine, the Omicron XBB.1.5 NVX-CoV2601 in immunosuppressed populations.

2024-2025 season (The 2024-2025 season activities will not proceed as originally planned due to the withdrawal of financial support from our sponsor).
 The primary objective of this study is to evaluate the immunogenicity of a 2024/2025 (monovalent, XBB containing) Novavax COVID-19 vaccine, the Omicron XBB.1.5 NVX-CoV2601 in immunosuppressed populations.

6.1 Primary Objective

The following objective will be evaluated separately based on the season 2023-2024 and 2024-2025.

Humoral Immunogenicity of a NVX-CoV2601/(2024/2025 COVID booster).

We will evaluate antibody concentrations 1 month after the recombinant vaccine booster (V2) in patients with IBD and solid organ transplant recipients compared to their baseline visit (V1). We measured antibody concentrations in patients with IBD one-month post-booster and found robust responses. We will measure anti-receptor binding domain (RBD) antibody levels and nucleocapsid antibodies in all participants at baseline and post-immunization.

Success Criterion: The objective of our primary endpoint will be achieved if the antibody concentration at V2 is at least 15% higher than at V1.

6.2 Secondary objectives

The vaccine will be evaluated for two seasons, separately: 2023/2024 and 2024/2025. Thus, we will have two co-secondary objectives.

6.2.1 Sustained antibody concentrations of NVX-CoV2601 booster dose/(2024/2025 COVID booster).

We will evaluate sustained antibody concentrations using a quantitative assay from LabCorp, which is currently being used by the Centers for Disease Control and Prevention (CDC) to evaluate seroprevalence and study immunity at six months after completion of the booster dose (V3).

Endpoint:

We will evaluate individuals who are seropositive at V2 and V3 in both groups.

Seropositivity rate at V2 and V3 in all participants.

Seropositive will be defined by positive anti-receptor binding domain (RBD) IgG antibodies specific to SARS-CoV-2 performed by Labcorp (greater than 1.0 in µg/mL).

Success Criterion: Descriptive

6.2.2 Seroconversion.

Percentages (and 2-sided 95% Cis) of participants who were seronegative (less than 1.0 in $\mu g/mL$) at baseline and became seropositive (greater than 1.0 in $\mu g/mL$) after immunization will be evaluated for before and after measures. For initially seropositive subjects at V1, antibody concentration at post-vaccination (V2) \geq 4 fold the pre-vaccination antibody concentration.

Endpoint:

Individuals who achieve seroconversion at V2.

Success Criterion: Descriptive

6.2.3 Cell-mediated immunity to NVX-CoV2601/(2024/2025 COVID booster). **COVID-19** booster vaccine.

We will evaluate cell-mediated immunity to a booster dose vaccine at baseline (V1) and one month after a booster dose (V2) in patients with IBD and solid organ transplant recipients. IFN-Y ELISpot, which detects both CD4 and CD8 T cell effectors, will be used to detect T-cell immunity to the Covid-spike protein or peptides.

Endpoint:

We will evaluate the interferon gamma responses at V2 compared to V1.

An interferon gamma response will be considered any measurable response.

Success Criterion: Descriptive

6.2.4 Sustained cell-mediated immunity to NVX-CoV2601/(2024/2025 COVID booster). **COVID-19 booster vaccine.**

We will evaluate sustained cell-mediated immunity against Covid-spike proteins approximately six months following V1 (V1 + 180 days, +/-30 days) (V3)

Endpoint:

We will evaluate the interferon gamma responses at V3 compared to V1.

Success Criterion: Descriptive

The safety of the vaccine boosters will be assessed for both seasons separately. This includes section 6.3-6.5.

6.3 Describe the safety of NVX-CoV2601/(2024/2025 COVID booster). COVID-19 vaccine.

Participants will be asked to fill out their vaccine diary daily for 7 days post immunization. They will record the information daily for 7 days post immunization.

Participants will be provided a paper vaccine diary on visit 1 to enter their answers.

At follow up visit 1 the research coordinator will remind patients to complete their diary. If they have lost the diary the coordinator will fill out the diary with participant.

At follow up visit 1 they will be asked about any unsolicited or solicited adverse events occurred following immunization. The call will involve standardized list of potential adverse effects, including fever, injection site reaction, fatigue, myalgia, and other reactions not listed.¹⁸ Participants who do not fill out their vaccine diary or unable to be contacted at FU1 will be considered to have missing post immunization data. This data will be considered non-reported data.

Participants will be asked about unsolicited and solicited adverse events at all study visits V1, V2, and V3.

Safety and reactogenicity up to 30 days post-last vaccination and during the whole post-vaccination follow-up period

Endpoints:

Solicited Adverse Events (AEs)

The number and percentage of participants reporting each solicited local AE and each solicited systemic AE within seven days (Days 1-7) after the booster dose and overall will be summarized for both study groups.

- Solicited local AEs included injection site pain, redness, and swelling.
- Solicited systemic AEs included fatigue, myalgia, arthralgia, headache, shivering/chills, fever, and gastrointestinal symptoms (nausea, vomiting, diarrhea, and abdominal pain).

Success Criterion: Descriptive

Unsolicited Adverse Events

The number and percentage of participants reporting unsolicited AEs within 30 days (Days 1-30) after the booster dose and overall will be summarized for both the study groups.

Success Criterion: Descriptive

Potential Immune-Mediated Diseases (pIMDs)

The number and percentage of participants reporting pIMDs from the booster dose to the study end will be summarized for both study groups. Please refer to the full list of pIMD's in Appendix 3

Success Criterion: Descriptive

Serious Adverse Events (SAEs)

The number and percentage of participants reporting SAEs and fatal SAEs from the booster dose administration to the study end will be summarized for both the study groups.

Success Criterion: Descriptive

6.4 Evaluate the disease activity following administration of the booster dose up to 30 days post-vaccination and during the whole post-vaccination follow-up period.

Disease activity will be assessed by monitoring disease activity using the Short Crohn's Activity Index (SCAI)¹⁹ for patients with Crohn's disease or the Simple Clinical Colitis Activity Index (SCCAI) questionnaire for patients with Ulcerative colitis at the baseline visit (V1), V2, and V3 visits. For patients with pouchitis we will use the simplified pouchitis disease activity index (PDAI). The incidence of IBD flares will be evaluated in all patients receiving recombinant boosters. This will be quantified by patients who were in clinical remission who develop a disease flare after receiving a recombinant COVID-19 booster.

Endpoint:

The number and percentage of participants reporting disease flares of IBD.

Success Criterion: Descriptive

6.5 Evaluate for solid organ transplant rejection following administration of booster dose, up to 30 days post-vaccination and during the whole post-vaccination follow-up period.

Participants will be asked if they have been diagnosed with acute rejection after their baseline visit (V1). Episodes of acute rejection will be collected by searching electronic medical records and asking patients at each clinic visit (V2 and V3). Acute rejection will be defined as a notation of a new episode of acute rejection (cellular or antibody-mediated), a steroid bolus and taper in the absence of another indication, or administration of a T or B cell depleting agent or immune globulin.²⁰

This will be quantified by patients who develop acute rejection of their transplant after receiving a recombinant COVID-19 booster.

Endpoint:

The number and percentage of participants reporting acute rejection of their transplant.

Success Criterion: Descriptive

[figure not shown]

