8.2 Exclusion criteria

A patient will not be eligible for inclusion in this study if they meet any of the following criteria.

- Allergy to recombinant COVID-19 vaccine or any component of it
- Patient cannot or will not provide written informed consent.
- Unable to provide appropriate informed consent because of illiteracy or impairment in decision-making capacity.
- Active antibody-mediated or cellular rejection within the past six months
- Recent IBD flare requiring initiation of systemic corticosteroids within the past month
- Previous history of myocarditis or pericarditis ever.
- Patients who are pregnant
- Patients who are lactating
- Patients with an active COVID-19 infection
- Patients with a COVID-19 infection within the past two months

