10.0 STUDY ASSESSMENT SCHEDULE AND PROCEDURES

10.1 Study Calendar

Procedure (Visit Window)	Visit 1 (V1) (Day 0)	F/U 1 ⁵ (Day 7-15)	Visit 2 (V2) (Day 28-65)	Visit 3 (V3) (V1 + 180 days +/- 30 days)
Informed Consent	X			
Demographics	Χ			
Concomitant Medications	X		Х	Х
Medical History ¹	Χ			
Inclusion/Exclusion Criteria	Х			
Blood draw (Serum & CMI)	X		X	Х
Standard of Care Recombinant COVID-19 Vaccine Booster	X			
7-Day Vaccine Diary ²	X			
SCAI, PDAI, or SCCAI Questionnaire ³	Х		Х	х
Adverse Event Monitoring	Х	Х	Х	Х
Telephone Contact ⁴		Χ		

Notes:

- 1. Baseline medical history included all IBD diagnoses or solid organ transplant diagnoses, medication history, and information in the source documents.
- 2. Dispense the 7-day Vaccine Diary at Visit 1 for subjects to complete at home.
- 3. SCAI, PDAI, or SCCAI will be administered based on IBD diagnosis at visits 1, 2, and 3.
- 4. Between Visit 1 and Visit 2, the study staff will attempt two phone contacts to assess AEs and remind them to complete vaccine diaries as well as to assist with subject retention.
- 5. Visits can be conducted via telephone calls. Patients who don't respond to survey will be emailed and receive a phone call reminding them to fill out diary.

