10.4.2 Disease Activity Assessment

The Short Crohn's Activity Index (SCAI), the Simplified Pouchitis Disease Activity Index (PDAI), or the Simple Clinical Colitis Activity Index (SCCAI) questionnaire will be used to assess CD, Pouchitis, or UC disease activity, respectively (**Appendices 1 and 2**). These assessments include questions about patient overall well-being as well as specific symptoms and complications of CD or UC, such as stool frequency and abdominal pain.

Subjects will be questioned at each visit, V1, V2, and V3, regarding their clinical symptoms and subsequently scored accordingly.

Transplant Rejection

Episodes of acute rejection will be collected by searching electronic medical records and asking patients at each clinic visit V1, V2, and V3. Acute rejection will be defined as a notation of a new episode of acute rejection (cellular or antibody-mediated), a steroid bolus and taper in the absence of another indication, or administration of a T or B cell depleting agent or immune globulin.

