14.0 RISK-BENEFIT

14.1 Risks of Study

The risks to subjects in this trial will be minimized by compliance with the eligibility criteria, clinical monitoring, adherence to protocol requirements, and investigator guidance regarding specific safety areas.

Appropriate medical treatment will be available to manage immediate allergic reactions in the event an acute anaphylactic reaction occurs following administration of the Novavax COVID-19 Vaccine, Adjuvanted.

Adverse reactions reported in clinical trials following administration of the Novavax COVID-19 Vaccine, Adjuvanted include injection site pain/tenderness, fatigue/malaise, muscle pain, headache, joint pain, nausea/vomiting, injection site redness, injection site swelling, fever, chills, injection site pruritus, hypersensitivity reactions, lymphadenopathy-related reactions, myocarditis, and pericarditis.

Myocarditis, pericarditis, anaphylaxis, paresthesia, and hypoesthesia have been reported following administration of the Novavax COVID-19 Vaccine, Adjuvanted outside of clinical trials.

The rate of IBD flares or solid organ transplant rejections will be evaluated in the study populations following the administration of the Novavax COVID-19 vaccine.

To ensure subject privacy, the study procedures will be performed in a private room. The study team members will be in a private space when conducting study phone/video calls with potential participants.

The specific safety areas that will be closely monitored in this subject population are the risk of flares post-immunization and the rates of transplant rejection.

Loss of confidentiality: There is a risk that the subject information could become known to someone not involved in this study.

Phlebotomy: Blood draws can cause bruising in the skin at the injection site and, rarely, infection in the skin. Rarely, dizziness or fainting occurs after blood is drawn.

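### Section 6.4 scores disease activity at three visits but quantifies only flares from remission, so no change in index score or category is reported and worsening in participants active at V1 falls outside its count

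*Combined protocol and SAP*

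**What the plan says.** The objective in section 6.4 is to evaluate disease activity up to 30 days after the booster and over the whole follow-up. The data are serial: the study calendar (10.1) states "SCAI, PDAI, or SCCAI will be administered based on IBD diagnosis at visits 1, 2, and 3", and section 10.4.2 adds "Subjects will be questioned at each visit, V1, V2, and V3, regarding their clinical symptoms and subsequently scored accordingly".

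On who is counted, section 6.4 has two consecutive sentences. One is "The incidence of IBD flares will be evaluated in all patients receiving recombinant boosters". The next is "This will be quantified by patients who were in clinical remission who develop a disease flare after receiving a recombinant COVID-19 booster". The endpoint line is "The number and percentage of participants reporting disease flares of IBD", with a descriptive success criterion. The synopsis endpoint is also a number and percentage with flares, with no remission condition.

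Section 12.2 promises descriptive statistics and exploratory tests for the secondary endpoints, and a formal SAP before database lock. It names no summary of the index scores.

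Remission is not among the inclusion criteria in 8.1. The only exclusion in 8.2 that bears on IBD activity is "Recent IBD flare requiring initiation of systemic corticosteroids within the past month". Section 14.1 gives flares prominence: "The specific safety areas that will be closely monitored in this subject population are the risk of flares post-immunization and the rates of transplant rejection".

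**The concern.** The objective is about disease activity, but the stated quantification is about one transition, from remission to flare. A participant who enters with mild activity and becomes severe has moved in exactly the direction that 14.1 singles out, yet does not fit the 6.4 definition. A participant who deteriorates within the remission band does not fit it either.

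At stake is what the report can say. With few IBD participants the likeliest flare count is zero. On its own that would say little about disease activity, although the scores that could describe it are in the database. The two sentences on who is counted also leave the numerator and denominator of the reported percentage open.

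**Working it through.** The plan states no power or precision figure for this objective, and section 12.1 says no formal sample size was calculated, so there is nothing to reproduce.

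**1. Movement outside the 6.4 count, using the appendix bands**

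Section 6.4 gives no score cut-off for a flare. Treating departure from the remission band as the boundary is an inference from the appendices.

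- SCCAI (Appendix 2): maximum 3 + 2 + 3 + 3 + 4 + 4 = 19, which agrees with the stated 19. Remission is 0 to 4 and mild is 5 to 7. A score can rise from 0 to 4 within remission. A participant at 5 at V1 can rise to 19 without meeting the remission condition.
- sCDAI (Appendix 1): minimum 44; remission is below 150. With constant daily ratings, 5 liquid stools, pain 1 and well-being 0 give 44 + 2×35 + 5×7 + 7×0 = 149. A rise of 149 − 44 = 105 points is therefore possible within remission. A participant at 150 to 219 at V1 can pass 450 without meeting the remission condition.
- PDAI (Appendix 2b): only two bands, below 6 and 6 or more. The items visible in the text sum to 2 + 1 + 2 + 1 = 6, though the table may be incomplete as extracted. A participant already at 6 or more has no worse category to move into.

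**2. How informative the flare count is**

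Inputs: 21 enrolled and no further recruitment (synopsis); a 2% flare rate after earlier COVID-19 vaccines in IBD (5.1). The IBD share is not stated, so I assume 8 to 15, all in remission at V1.

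P(no flare) = (1 − p)^n. The exact two-sided 95% upper bound for 0/n is 1 − 0.025^(1/n).

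| n at risk | P(no flare), p = 2% | Upper bound if 0/n |
|---|---|---|
| 8 | 0.98^8 = 85% | 36.9% |
| 10 | 0.98^10 = 82% | 30.8% |
| 12 | 0.98^12 = 78% | 26.5% |
| 15 | 0.98^15 = 74% | 21.8% |

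At a true rate of 10%, P(no flare) is still 0.9^8 = 43% to 0.9^15 = 21%.

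If fewer are in remission, fewer are at risk. With 10 IBD participants of whom 6 are in remission, the bound for 0/6 is 1 − 0.025^(1/6) = 45.9%. The documents give no V1 remission share, so the number of participants left out of the count cannot be estimated.

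**3. What the two sentences do to the percentage**

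In the same hypothetical, one flare from remission is 1/6 = 17% of those in remission, 1/10 = 10% of IBD participants and 1/21 = 5% of all enrolled. If flares in active participants also count, the numerator changes too.

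**The case against.** A reader might infer that worsening in participants active at V1 is never reported, or that the flare count is the plan's only use of the indices. The documents do not support either reading:

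- Section 13.23 has deterioration of a condition present at screening recorded as an AE, with changes in severity documented.
- Section 13.21 lists IBD flares among the events of special interest, judged on the same three indices, with no remission condition.
- Section 13.11 puts AEs, SAEs and events of special interest into a summary table, and 6.3 tabulates unsolicited AEs to Day 30 and overall.
- The stopping rule in 13.26 counts flares of at least moderate activity without a known cause, whatever the V1 state.

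So a move from mild to severe could well reach the safety tables. What remains is narrower. These routes depend on someone calling the change an AE or a flare. No section says what a flare is in a participant already active at V1, and no rule links a rise in score to an AE. None of the routes produces a summary of the index, which is what the 6.4 objective calls for. The 6.4 count and the special-interest table could also give two different flare totals.

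A second tempting reading is that analysing the scores would bring useful precision or power. It would not. The three indices are on different scales and must be kept apart; 8 to 15 participants over three indices average about 3 to 5 each. The 95% half-width for a mean change, t(0.975, n−1)/√n, is 2.48 SD at n = 3 and 1.24 SD at n = 5. The gain is description only.

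It is also fair that the formal SAP is still to come and could add these summaries. Silence here is a gap in this document, not proof that the scores will go unused.

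**Conclusion.** The point holds as a minor gap in descriptive safety reporting. Section 6.4 collects serial scores, quantifies only flare from remission, and admits participants to whom that definition cannot apply. Neither 6.4 nor 12.2 plans a change-in-score or change-in-category summary. Section 6.4 is also inconsistent on whether all boosted patients or only those in remission are counted.

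The most likely 6.4 result is zero flares (85% to 74% at a 2% rate), compatible with true rates up to 36.9% to 21.8%, and higher if fewer are in remission at V1. These figures rest on three assumptions: 8 to 15 IBD participants, all in remission at V1, and the 2% background rate applying here. They show how little a zero count says; they do not measure how much worsening would be missed, which the documents do not allow one to estimate. The primary endpoint is unaffected.

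**What to change.** Keep the flare count and reconcile the two sentences in 6.4 on who is counted, so that numerator and denominator are explicit and consistent with 13.21.

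Add to 6.4 and to the forthcoming SAP, descriptively and for each index separately:

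- change in score from V1 to V2 and from V1 to V3: median, range and individual values;
- a table of V1 category against V2 and V3 category, on the appendix bands, for all IBD participants with scores;
- the number worsening by at least one category, whatever the V1 category. For the PDAI, the change in score carries the information for anyone already in the upper band.

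State how many IBD participants have scores at each visit. Indeterminate colitis is eligible under 8.1, but 6.4 and 10.4.2 assign it no index.

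No confidence intervals or tests on the score changes are needed. The cost is SAP wording and a short set of descriptive tables; no new data are collected and clinical management does not change. The drawback is that each index will have only a few participants, so the tables should be read as individual-level description.
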